4.10 Supportive Care Guidelines

Participants will follow their oncology care plan. All medications required as part of a participant's normal clinical care for support of their medical conditions are permitted during the study, except for prohibited medications listed below. All concomitant medications must be recorded in the source documentation and in the CRFs for the duration of patient participation.

The following medications/treatments are prohibited during the study:

- Another investigational drug;
- Strong Cytochrome P450 subtype 3A4 (CYP3A4) inhibitors (such as but not limited to, atazanavir, clarithromycin, indinavir, itraconazole, ketoconazole, nefazodone, nelfinavir, ritonavir, saquinavir, telithromycin, troleandomycin, voriconazole, and grapefruit juice) or strong CYP3A4 inducers (such as but not limited to, rifampin, carbamazepine. rifapentine, phenytoin, phenobarbital, and St. John's wort or hyperforin).

Version: Amendment 4 Date: 31 Mar 2020

Protocol Number: NVGN-0084-201

IND Number: 112,608

Enzyme-inducing anti-epileptic drugs should also be avoided. If use of such drugs is necessary, the risks and benefits should be discussed with the medical monitor prior to its concomitant use with GDC-0084.

Based on nonclinical toxicology findings for GDC-0084, known toxicities associated with PI3K and mTOR inhibitors (including rapamycin analogues) in the clinic, and clinical safety data from study G028070, the guidelines for monitoring and management of specific toxicities detailed below should be considered.

4.10.1 Hyperglycemia and Metabolic Effects

It is known that PI3K-mTOR pathway inhibitors can affect glucose and/or insulin metabolism, leading to hyperglycemia. Cases of hyperglycemia, including Grade 3 in severity, have been observed in the GDC-0084 single-agent study GO28070. Glucose levels at baseline and during study should be carefully monitored, and appropriate dose delays/dose modifications for managing hyperglycemia should be implemented per protocol quidelines. Patients should be instructed to report symptoms associated with hyperglycemia such as thirst, frequent urination, and blurred vision. Use of oral anti-hyperglycemic agents, such as metformin, for patients experiencing Grade ≥ 2 hyperglycemia may be implemented. Anti-hyperglycemic agents should be used to control severe hyperglycemia per institutional standard of care.

Other metabolic effects known to be associated with mTOR inhibitors include hyperlipidemia. Cases of low-grade hypercholesterolemia and hypertriglyceridemia have been observed in the GDC-0084 single-agent study GO28070. Cholesterol and triglyceride levels should be monitored per protocol guidelines. Use of lipid-lowering therapy for patients experiencing Grade ≥ 2 elevations may be initiated per institutional standard of care and protocol guidelines.

4.10.2 Potential Lung Inflammation/Pneumonitis

Lung inflammation was not observed in any of the rat studies and was not observed in the 29-day dog study. Evidence of lung inflammation was observed in the 8-day dog pilot study. However, this finding was observed only at doses exceeding the MTD in this species. Interstitial lung inflammation/noninfectious pneumonitis has been observed in cancer patients receiving other PI3K and mTOR inhibitors. Patients should be monitored carefully for changes in pulmonary status (including physical examinations, pulse oximetry, and periodic CT scans) during treatment with GDC-0084. Patients experiencing symptomatic or asymptomatic pneumonitis should be treated per standard of care and protocol guidelines adapted from recommendations by (White, Camus et al. 2010) for the management of pneumonitis in cancer patients receiving everolimus. Use of corticosteroids should be considered for symptomatic cases of non-infectious pneumonitis. Appropriate dosing adjustment should be performed per protocol guidelines.

4.10.3 Gastrointestinal Tract Toxicities

In the IND-enabling toxicology studies of GDC-0084, dose-limiting gastrointestinal inflammation and degeneration were observed. As a class effect, PI3K and mTOR inhibitors have been associated with GI effects including stomatitis/oral mucositis, nausea, vomiting, diarrhea, and colitis. Although rare, cases of fatal bowel perforation have been reported in patients who received temsirolimus. Nausea, vomiting, and diarrhea have been reported in patients receiving single-agent GDC-0084 in Study GO28070. Grade 3 mucosal inflammation was also reported for a patient dosed with 45 mg GDC-0084 and two patients dosed with 65 mg GDC-0084 in Study GO28070. GI effects should be closely monitored by physical examination and symptom and laboratory evaluations. Development of stomatitis/oral mucositis, abdominal pain, nausea, vomiting, and clinically significant changes in stool (e.g., diarrhea, bloody stools) may necessitate more frequent monitoring, and study drug may be held if symptoms are prohibitive for normal function.

Gastrointestinal toxicities will be managed according to institutional standard-of-care and protocol guidelines. During the study, patients are to receive maximum supportive care as clinically indicated. Maximum supportive care for nausea and vomiting may include standard-of-care symptom management. Maximum supportive care for diarrhea should include standard-of-care treatment with anti-motility therapy and dietary adjustments. Additionally, supplemental intravenous fluids are

Version: Amendment 4 Date: 31 Mar 2020

Protocol Number: NVGN-0084-201

IND Number: 112.608

permitted. Patients experiencing mucositis/stomatitis should also treated as per standard of care. In addition, sites should consider using an alcohol-free dexamethasone 0.5 mg per 5mL oral solution (elixir) if such symptoms eventuate. Patients may be instructed to use 10ml oral solution swished for up to two minutes and then spit, up to four times daily (Rugo et al. 2017).

4.10.4 Potential Skin Disorder

Treatment-related rash has been commonly reported in cancer patients receiving other PI3K and mTOR inhibitors in clinical studies. This rash is commonly manifested as maculo-papular with or without pruritus. Rash and other dermatologic events should be closely monitored, and patients should apply Sun Protection Factor 50+ sunscreen if exposed to direct sunlight for longer than 15 minutes after the appearance of any rash. For severe rash, dosing of GDC-0084 should be interrupted and patients should be treated with supportive therapy per standard of care. Use of topical antihistamine, as well as topical or systemic corticosteroids, may be considered.

4.10.5 Potential Hematological or Immunosuppressant Effects

As a result of observed changes in WBC count and absolute lymphocyte count in nonclinical toxicology studies with GDC-0084, patients will be required to have adequate hematologic function to enter the study and bone-marrow toxicities from prior therapies must be resolved before initiation of GDC-0084. Patients will be monitored routinely for changes in circulating blood cell counts, including a WBC count with differential. Because of the known immunosuppressive activity of mTOR inhibitors, patients who are immunocompromised as the result of human immunodeficiency virus will be excluded from the study. Many patients with high-grade gliomas will have received prior TMZ, a therapy that frequently causes lymphopenia. Such patients will be able to enroll in the trial and will be monitored closely for opportunistic infections. Prophylactic antibiotics such as sulfamethoxazole/trimethoprim are encouraged when the absolute lymphocyte count is < 500/µL. The decision to initiate prophylactic antibiotics should be discussed with the medical monitor.

4.10.6 Potential Cardiac Effects

One patient receiving 15 mg GDC-0084 QD in Cohort 4 of study GO28070 experienced an AE of Grade 2 bradycardia and Grade 3 myocardial ischemia, and 1 patient receiving 30 mg GDC 0084 QD in Cohort 6 experienced an event of Grade 2 myocardial infarction. Both patients developed asymptomatic cardiac ischemia accompanied by troponin elevations and ECG T-wave inversions. One subject dosed at 30 mg GDC-0084 had a QTcF value marginally greater than 450 msec at 24 h after dosing, and five subjects had QTcF increases of > 30 msec above baseline on at least one occasion, but no QTcF increases > 60 msec were recorded.

Analysis of the relationship between GDC-0084 plasma concentrations and QTcF showed a slight positive trend for absolute QTcF and QTcF change from baseline. Based on this limited sample size. GDC-0084 has the potential to prolong the QTc interval. Patients with QTc interval > 470 msec will be excluded from this study and a specific, detailed QT and overall cardiac risk mitigation plan will be observed for phase 2.

Patients with significant cardiac history (e.g., myocardial infarction or symptomatic bradycardia, active congestive heart failure, and angina pectoris) should be excluded from study participation. During the study, patients should be instructed to contact their treating physician if they experience dizziness, light-headedness, fainting, sensations of heart palpitations, or slow or irregular pulse. Electrocardiograms should be closely monitored. Cardiac enzymes may be measured if deemed necessary.

4.11 Criteria for Removal from Study

4.11.1 Removal of Patients

Patients will be advised in the Informed Consent Form (ICF) that they have the right to withdraw from the study at any time without prejudice, and may be withdrawn at the Investigator's, the contract research organization's (CRO's) or Kazia Therapeutics Limited's discretion at any time. If a patient

Version: Amendment 4 Date: 31 Mar 2020

Protocol Number: NVGN-0084-201

IND Number: 112.608

drops out of the study or is withdrawn from the study, the withdrawal form in the patient's CRF should be completed and all study drug supplies should be retrieved. On the withdrawal page the Investigator should record the date of the withdrawal, the person who initiated withdrawal and the reason for withdrawal.

Reasonable effort should be made to contact any patient lost to follow up during the course of the study in order to complete assessments and retrieve any outstanding data and study medication/supplies.

The following are reasons for patient withdrawal:

Withdrawn by the Investigator due to:

- Protocol deviation (e.g. dosing regimen, failure to comply with clinic visit schedule);
- · Administration of an excluded medication;
- Co-existing disease;
- Worsening of condition;
- Pregnancy;
- Clinically significant abnormal laboratory value(s).

The patient requested withdrawal due to:

- An AE for which the Investigator did not consider removal from the study necessary;
- Perceived insufficient therapeutic effect:
- Co-existing disease:
- Withdrawal of consent.

Other reasons for withdrawal may include:

- Patient died;
- Kazia Therapeutics Limited/CRO request the patient to be withdrawn;
- Lost to follow-up;
- Administrative problems.

Withdrawals will only be replaced in the dose finding/MTD portion (Stage 1) of the phase 2a study to ensure that a full cohort is available at the time of CRC review.

4.11.2 Definition of Dose-Limiting Toxicity

Toxicities will be graded according to the NCI CTCAE v4.03. If a patient experiences one of the below, study participation will be terminated for this patient and the EoT visit should be performed.

For dose-escalation purposes, DLT assessments will be performed by the Kazia Therapeutics Limited in consultation with the Investigators during CRC meetings. A DLT is defined as any one of the following toxicities occurring within the DLT assessment window (Cycle 1, Days 1 - 28) and assessed by the Investigator to be related to GDC-0084.

Details on DLTs are given in Section 3.7.1.

4.11.3 Premature Discontinuation of Study in a Study Site

Kazia Therapeutics Limited reserves the right to discontinue the study at any time. The reasons will be discussed with the Investigator. A study site may also be discontinued by Kazia Therapeutics Limited for significant deviations from the protocol or due to difficulties experienced in running the study at that site.

Kazia Therapeutics Limited may terminate this study at 1 particular or several study sites for 1 of the following reasons:

- Non-compliance with Good Clinical Practice (GCP) and/or regulatory requirements;
- Site cannot recruit an adequate number of patients;
- False documentation in the CRF due to carelessness or deliberately;

Protocol Number: NVGN-0084-201 Version: Amendment 4 IND Number: 112.608 Date: 31 Mar 2020

Inadequate co-operation with Kazia Therapeutics Limited or its representatives;

The Investigator requests closure of his/her study site.

If the study is prematurely terminated at 1 or more sites, all Investigators have to inform their patients and take care of appropriate follow-up and further treatment. IRBs and regulatory authorities will be informed about the reason and time of termination according to the applicable laws and regulations.

4.11.4 Sponsor Premature Discontinuation Criteria

Premature termination of this study may occur because of a regulatory authority decision, change in opinion of the IRB, drug safety problems, or at the discretion of Kazia Therapeutics Limited. In addition, Kazia Therapeutics Limited retains the right to discontinue development of GDC-0084 at any

A decision to prematurely discontinue the study is binding to all Investigators of all study sites. IRBs and regulatory authorities will be informed about the reason and time of termination according to the applicable laws and regulations. If the study is terminated prematurely, all Investigators have to inform their patients and arrange for appropriate follow-up and further treatment.

4.11.5 Definition of End of Study

End of the study in all participating sites and countries is defined as the date the last patient completes the follow-up post End of Treatment visit. Kazia Therapeutics Limited will notify IRBs and regulatory authorities about the regular termination of the study as required according to national laws and regulations.

5 Adverse Event Reporting

5.1 **Adverse Events**

All observed or volunteered AEs regardless of treatment group or suspected causal relationship to the investigational medicinal product will be reported as described in the following sections. All AEs will be collected in response to a general question about the patient's well-being and any possible changes from the baseline or previous visit, but shall not be specifically solicited with respect to particular AEs.

For all AEs, the Investigator must pursue and obtain information adequate both to determine the outcome of the AE and to assess whether it meets the criteria for classification as an SAE requiring immediate notification to Kazia Therapeutics Limited or its designated representative. For all AEs, sufficient information should be obtained by the Investigator to determine the causality of the AE. The Investigator is required to assess causality. AEs will be followed until resolved, stable, or until the patient's last study visit or is lost to follow-up. If an AE is not resolved or stabilized at the patient's last visit, it is up to the discretion of the Investigator and Kazia Therapeutics Limited's medical monitor to determine if further monitoring of the event is warranted.

As part of ongoing safety reviews conducted by Kazia Therapeutics Limited, any non-serious AE that is determined by the sponsor to be serious will be reported by Kazia Therapeutics Limited as an SAE. To assist in the determination of case seriousness, further information may be requested from the Investigator to provide clarity and understanding of the event in the context of the clinical study.

5.2 Reporting Period

For AEs, the active reporting period to Kazia Therapeutics Limited or its designated representative begins from the time that the patient provides informed consent, which is obtained prior to the patient's participation in the study, i.e., prior to undergoing any study-related procedure and/or receiving investigational product, through and including 28 calendar days after the last administration of the investigational product, including administration during long term treatment.

Additionally, all SAEs brought to the attention of the Investigator during the period starting from the time the patient signed the ICF and ending not earlier than 28 days following administration of the last

Date: 31 Mar 2020

Protocol Number: NVGN-0084-201 Version: Amendment 4 IND Number: 112.608

dose of study drug for that patient must be reported. Disease progression and death will be reported as part of the study endpoints and not as AEs or SAEs unless there is unambiguous evidence that death was due to a cause other than disease under study.

5.3 Definition of an Adverse Event

An AE is any untoward medical occurrence in a clinical investigation patient administered a product or medical device; the event need not necessarily have a causal relationship with the treatment or usage. Examples of AEs include but are not limited to:

- Abnormal test findings (see section 5.4);
- Clinically significant symptoms and signs;
- Changes in physical examination findings:
- Hypersensitivity;
- Drug abuse:
- Drug dependency:
- Additionally, they may include the signs or symptoms resulting from:
 - Drug overdose:
 - Drug withdrawal:
 - Drug misuse;
 - Drug interactions;
 - Extravasation;
 - Exposure during pregnancy;
 - Exposure via breastfeeding;
 - Medication error.

Worsening of signs and symptoms of the malignancy under study should be reported as AEs in the appropriate section of the CRF. Disease progression and death will be reported as part of the study endpoints and not as AEs or SAEs unless there is unambiguous evidence that death was due to a cause other than disease under study.

5.4 Abnormal Test Findings

The criteria for determining whether an abnormal objective test finding should be reported as an AE are as follows:

- Test result is associated with accompanying symptoms; and/or
- Test result requires additional diagnostic testing or medical/surgical intervention; and/or
- Test result leads discontinuation from the study, significant additional concomitant drug treatment, or other therapy; and/or
- Test result considered to be an AE by the Investigator or sponsor;
- Merely repeating an abnormal test, in the absence of any of the above conditions, does not constitute an AE. Any abnormal test result that is determined to be an error does not require reporting as an AE.

5.5 Serious Adverse Events

An SAE is any untoward medical occurrence at any dose that:

- Results in death (when there is unmistakable evidence that death was due to a cause other than disease under study, otherwise death is report as a study endpoint);
- Is life-threatening (immediate risk of death);
- Requires inpatient hospitalization or prolongation of existing hospitalization;
- Results in persistent or significant disability/incapacity (substantial disruption of the ability to conduct normal life functions);
- Results in congenital anomaly/birth defect;
- Is determined to be an important medical event by the Investigator.

Progression of the malignancy under study (including signs and symptoms of progression) should not be reported as an SAE unless the outcome is fatal within the safety reporting period. Hospitalization

Date: 31 Mar 2020

Protocol Number: NVGN-0084-201 Version: Amendment 4 IND Number: 112.608

due to signs and symptoms of disease progression should not be reported as an SAE. Disease progression and death will be reported as part of the study endpoints and not as AEs or SAEs.

Events that are clearly consistent with the expected pattern of progression of GBM should not be recorded as AEs. These data will be captured as efficacy assessment data only. In most cases, the expected pattern of progression will be based on the RANO criteria. In rare cases, the determination of clinical progression will be based on symptomatic deterioration. However, every effort should be made to document progression using objective criteria. If there is any uncertainty as to whether an event is due to disease progression, it should be reported as an AE.

Medical and scientific judgment is exercised in determining whether an event is an important medical event. An important medical event may not be immediately life-threatening and/or result in death or hospitalization. However, if it is determined that the event may jeopardize the patient or may require intervention to prevent one of the other AE outcomes, the important medical event should be reported as serious.

Examples of such events are intensive treatment in an emergency room or at home for allergic bronchospasm; blood dyscrasias or convulsions that do not result in hospitalization; or development of drug dependency or drug abuse.

5.5.1 **Drug Induced Liver Injury**

Abnormal values in AST and/or ALT concurrent with abnormal elevations in total bilirubin that meet the criteria outlined below in the absence of other causes of liver injury are considered potential cases of drug-induced liver injury (potential Hy's Law cases) and should always be considered important medical events.

The threshold of laboratory abnormalities for a potential case of drug-induced liver injury depends on the patient's individual baseline values and underlying conditions. Patients who present with the following laboratory abnormalities should be evaluated further to definitively determine the etiology of the abnormal laboratory values:

- Patients with AST or ALT and total bilirubin baseline values within the normal range who subsequently present with AST or ALT ≥ 3 x ULN concurrent with a total bilirubin ≥ 2 x ULN with no evidence of hemolysis and an alkaline phosphatase $\leq 2 \times \text{ULN}$ or not available;
- For patients with preexisting ALT OR AST OR total bilirubin values above the upper limit of normal, the following threshold values should be used in the definition mentioned above:
- For patients with pre-existing AST or ALT baseline values above the normal range: AST or ALT \geq 2 x the baseline values and \geq 3 x ULN, or \geq 8 x ULN (whichever is smaller);
- For patients with pre-existing values of total bilirubin above the normal range: Total bilirubin increased by one time the ULN $or \ge 3$ x the lower limit of normal (whichever is smaller).

If able to do so, the patient should return to the investigational site and be evaluated as soon as possible, preferably within 48 hours from awareness of the abnormal results. This evaluation should include laboratory tests, detailed history and physical assessment. For oncology studies, the possibility of hepatic neoplasia (primary or secondary) should be considered. In addition to repeating AST and ALT, laboratory tests should include albumin, creatine kinase, total bilirubin, direct and indirect bilirubin, GGT, PT/INR, and alkaline phosphatase. A detailed history, including relevant information, such as review of ethanol, acetaminophen, recreational drug and supplement consumption, family history, occupational exposure, sexual history, travel history, history of contact with a jaundiced patient, surgery, blood transfusion, history of liver or allergic disease, and work exposure, should be collected. Further testing for acute hepatitis A, B, or C infection and liver imaging (e.g., biliary tract) may be warranted. All cases confirmed on repeat testing as meeting the laboratory criteria defined above, with no other cause for liver function test (LFT) abnormalities identified at the time should be considered potential Hy's Law cases irrespective of availability of all the results of the investigations performed to determine etiology of the abnormal LFTs. Such potential Hy's Law cases should be reported as SAEs.

Version: Amendment 4 Date: 31 Mar 2020

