- To assess the distribution of GDC-0084 within the brain by fluorodeoxyglucose-positron emission tomography (FDG-PET) analysis of tumor and normal brain tissue (expansion cohort and patients with measurable disease only).

Endpoints

Primary Safety Endpoint:

Dose limiting toxicities (DLTs).

Secondary Safety Endpoints:

- Treatment-emergent adverse events (TEAEs), Grade 3-5 TEAEs, serious adverse events (SAEs), fatal AEs, and TEAEs leading to GDC-0084 discontinuation or study withdrawal;
- Treatment-emergent Grade 3/4 clinical laboratory abnormalities;
- Changes and shifts from baseline in clinical laboratory, vital signs, and electrocardiogram (ECG) parameters;
- Change from baseline in corticosteroid use;
- Change from baseline in left ventricular ejection fraction (LVEF);
- Change from baseline in Karnofsky Performance Status (KPS);
- Concomitant medication use;
- Adherence to the dosing regimen.

Secondary Endpoints of Clinical Benefit:

- PFS measured from first dose in the dose-escalation portion (Stage 1) or from randomization in the cohort expansion portion of the study (Stage 2) to disease progression (RANO criteria) or death due to any cause:
- OS measured from first dose in the dose-escalation portion (Stage 1) or from randomization in the cohort expansion portion of the study (Stage 2) to death due to any cause;
- TTP measured from first dose in the dose-escalation portion (Stage 1) or from randomization in the cohort expansion portion of the study (Stage 2) to date of earliest disease progression according to RANO criteria.

Exploratory Endpoints:

- PFS measured from first dose in the dose-escalation portion (Stage 1) or from randomization in the cohort expansion portion of the study (Stage 2) to disease progression (modified RANO criteria) or death due to any cause;
- PK parameters including area under the curve from time 0 to last measurable time point (AUC_{0-last}) and/or area under the curve from time 0 to infinity (AUC_{0-inf}), maximum concentration (C_{max}), minimum concentration (C_{min}), time to reach C_{max} (T_{max}), t_{1/2}, apparent total clearance of the drug from plasma after oral administration (CL/F), and accumulation ratio for C_{max} and AUC (fed and fasting);
- Change in FDG-PET uptake in tumor and normal brain tissue (defined as normal brain tissue with similar cell type to tissue surrounding tumor) in response to GDC-0084 in patients with measurable disease;

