4.5 Endpoints

4.5.1 **Primary Endpoint**

The primary endpoint of this study is safety-related and is the occurrence of DLTs during the study.

Protocol Number: NVGN-0084-201

Secondary Endpoints 4.5.2

Secondary endpoints are related to both, safety and clinical benefit as listed below.

Secondary Safety Endpoints:

- Treatment-emergent AEs (TEAEs), Grade 3-5 TEAEs, serious adverse events (SAEs), fatal AEs, and TEAEs leading to GDC 0084 discontinuation or study withdrawal;
- Treatment-emergent Grade 3/4 clinical laboratory abnormalities;
- Changes and shifts from baseline in clinical laboratory, vital signs, and ECG parameters;
- Change from baseline in corticosteroid use;
- Change from baseline in LVEF;
- Change from baseline in KPS;
- Concomitant medication use;
- Adherence to the dosing regimen.

Secondary Endpoints of Clinical Benefit:

- PFS measured from first dose in the dose-escalation portion (Stage 1) or from randomization in the cohort expansion portion of the study (Stage 2) to disease progression (RANO criteria) or death due to any cause:
- OS measured from first dose in the dose-escalation portion (Stage 1) or from randomization in the cohort expansion portion of the study (Stage 2) to death due to any cause;
- TTP measured from first dose in the dose-escalation portion (Stage 1) or from randomization in the cohort expansion portion of the study (Stage 2) to date of earliest disease progression according to RANO criteria.

4.5.3 **Exploratory Endpoints**

Exploratory endpoints in this study are:

- PFS measured from first dose in the dose-escalation portion (Stage 1) or from randomization in the cohort expansion portion of the study (Stage 2) to disease progression (modified RANO criteria) or death due to any cause:
- PK parameters including area under the curve from time 0 to last measurable time point (AUC_{0-last}) and/or area under the curve from time 0 to infinity (AUC_{0-inf}), maximum concentration (C_{max}), minimum concentration (C_{min}), time to reach C_{max} (T_{max}), t_{1/2}, apparent total clearance of the drug from plasma after oral administration (CL/F), and accumulation ratio for C_{max} and AUC (fed and fasted);
- Change in FDG-PET uptake in tumor and normal brain tissue (defined as normal brain tissue with similar cell type to tissue surrounding tumor) in response to GDC-0084 in patients with measurable disease:

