The exploratory endpoint DCR is defined as the proportion of patients achieving a confirmed BOR of CR, PR or SD according to a) RANO criteria and b) modified RANO criteria. BOR is defined as the best response recorded from first dose (Stage 1) or randomization (Stage 2) until progressive disease , death, withdrawal of consent or end of study, whichever occurs first. To be assigned a status of CR, PR or SD, the response must be confirmed by repeat assessments that should be performed no less than 28 days after the criteria for response are first met, i.e., patients need to have two consecutive assessments of CR, PR or SD. To be assigned a BOR of SD patients must have a minimum duration of SD of at least 6 weeks.

The number and proportion of responders and non-responders based on objective response rate and DCR will be presented with 95% Clopper-Pearson Cls. Further, objective response rate and DCR will be compared between treatment arms using Fisher's exact test. The difference in the proportion of responders and corresponding 95% CI (based on the Hauck-Anderson approach) will also be displayed.

Analyses of PFS will be repeated using modified RANO criteria.

Additional exploratory analyses of the data will be conducted as deemed appropriate.

6.3.5 **Safety Analysis**

All safety analyses will be conducted in the safety population.

AEs will be coded according to the Medical Dictionary for Regulatory Activities (MedDRA). The severity of AEs will be graded according to the United States NCI CTCAE, version 4.03.

TEAEs are defined as any AE occurring or worsening on/after the first study drug dose and within 28 days after the last dose date. TEAEs leading to study drug discontinuation, TEAEs leading to dose reduction/interruption, TEAEs related to study drug, SAEs, TEAEs leading to study drug discontinuation, and TEAEs with an outcome of death will be summarized by system organ class, and preferred term. Disease progression and death will be reported as part of the study endpoints and not as AEs or SAEs. A summary of TEAEs of NCI CTCAE Grade 3 or higher, as well as the most frequent TEAEs (preferred terms) by grade, and TEAEs by relationship to study treatment, will be provided. Additionally, a summary will be done for AEs using the worst grade of the event.

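### Sections 2.1, 4.8, 5.2, 5.3, 5.5 and 6.3.5 give incompatible rules on whether deaths and signs of progression are AEs or SAEs, so the fatal-AE endpoint depends on which sentence is followed

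*Combined protocol and SAP*

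**What the plan says.** On deaths, the protocol contains three rules.

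- **Rule A, no exception.** Section 6.3.5 states: "Disease progression and death will be reported as part of the study endpoints and not as AEs or SAEs". The synopsis (2.1, safety analysis) and a closing sentence in Section 5.5 say the same, and Section 4.8 says it in nearly the same words.
- **Rule B, a narrow exception.** Sections 5.2 and 5.3 state Rule A but add "unless there is unambiguous evidence that death was due to a cause other than disease under study". The first SAE criterion in 5.5 sets an equivalent test in slightly different words.
- **Rule C, fatal progression.** Section 5.5 says progression of the tumor "should not be reported as an SAE unless the outcome is fatal within the safety reporting period".

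On uncertain cause, 5.5 adds: "If there is any uncertainty as to whether an event is due to disease progression, it should be reported as an AE".

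On signs and symptoms, 5.3 says: "Worsening of signs and symptoms of the malignancy under study should be reported as AEs". Section 5.5 says: "Events that are clearly consistent with the expected pattern of progression of GBM should not be recorded as AEs".

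The secondary safety endpoints in 4.5.2 include Grade 3-5 TEAEs, SAEs, "fatal AEs, and TEAEs leading to GDC 0084 discontinuation or study withdrawal". The synopsis lists the same items. Section 6.3.5 plans a summary of TEAEs whose outcome was death, in the same paragraph that states Rule A.

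**The concern.** Safety and tolerability is the primary objective, and fatal AEs are a named secondary safety endpoint. A site cannot follow all three rules, because 5.5 alone contains all of them. Two sites could report the same death differently while each complied with a sentence of the protocol.

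The most exposed case is a death of unclear cause. Rule B treats it as disease unless the contrary is plain, while the uncertainty sentence in 5.5 points the other way. Such deaths are plausible here: treatment runs until progression, so the 28 days after the last dose often cover the period just after progression. Section 4.10 also describes cardiac ischemia with this drug and fatal bowel perforation with a related agent.

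The separate SAP, which Section 6.3 ranks above the protocol's statistical text, can define tables. It cannot recover SAEs that sites were told not to report.

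**Working it through.** The plan states no figure to reproduce. The check applies each rule to each kind of death within the safety reporting period.

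| Kind of death | Rule A (2.1, 4.8, end of 5.5, 6.3.5) | Rule B (5.2, 5.3, first SAE criterion in 5.5) | Rule C (5.5) | Uncertainty sentence (5.5) |
|---|---|---|---|---|
| From progression | not an AE or SAE | not an AE or SAE | SAE | not relevant |
| Clearly from another cause | not an AE or SAE | AE or SAE | silent | not relevant |
| Cause uncertain | not an AE or SAE | not an AE or SAE | silent | event reported as an AE |

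No row gives the same answer throughout.

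Let p, o and u be the numbers of deaths in the three rows, with D = p + o + u. The number of deaths that enter the safety tables as fatal events is then:

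- Rule A taken alone: 0
- Rule B: o
- Rule B with the uncertainty sentence: o + u
- Rules B and C together: p + o
- Rules B and C with the uncertainty sentence: p + o + u = D

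The o + u and D lines assume that an uncertain event that proves fatal is recorded as an AE with a fatal outcome.

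**Signs and symptoms.** Section 5.3 reports worsening as an AE without limit. Section 5.5 excludes what is clearly expected progression and reports what is uncertain. The two agree on uncertain events and conflict on worsening that is clearly progression.

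**Windows.** SAE reporting in 5.2 runs from consent to at least 28 days after the last dose. The TEAE definition in 6.3.5 runs from first dose to 28 days after the last dose. They serve different purposes and should not be merged.

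**Scale, as illustration only.** One death in Stage 2 is 1/20 = 5 percentage points, or 1/10 = 10 points within a fed or fasted arm. Clopper-Pearson 95% intervals are 0/20: 0 to 16.8%; 1/20: 0.1 to 24.9%; 2/20: 1.2 to 31.7%. The upper limit for 0/20 is 1 − 0.025^(1/20) = 0.168.

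**The case against.** The best defense is that death is an outcome or an efficacy endpoint, not an event term. A fatal pneumonia would then stay a TEAE with a fatal outcome, and Rule A would only stop sites from entering death or progression as the event. Several places fit this reading: the planned summary of fatal TEAEs in 6.3.5, Grade 5 in Table 2 (5.7) and the procedure for fatal SAEs in 5.12.1. It stands as a likely intent. The protocol nowhere states it, however, and it does not reconcile Rule C with Rule B.

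A reader might infer from 6.3.5 that the fatal-AE count is zero by construction. The documents do not support that. It takes one sentence apart from the table planned in the same paragraph and from 5.7 and 5.12.1. What 6.3.5 shows is a conflict with itself.

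A reader might also infer that deaths of uncertain cause are certain to be lost. Rule B classifies the death, while the uncertainty sentence concerns the event, so the precipitating event may still be recorded. The presumptions conflict, but exclusion does not necessarily follow.

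Nor does the point carry to the primary endpoint. The DLT definition in 3.7.1 has its own attribution test and does not refer to these rules.

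Three further points on the other side are fair. The 5.3 and 5.5 conflict on symptoms is softened by the limits in 5.5, though 5.3 has none. All deaths enter OS, and patient listings are planned (6.3.3), so deaths themselves are not hidden. OS counts any cause, however, and does not settle which deaths are safety events. Finally, the separate SAP is not among the documents, so the final tabulation rule is unknown.

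**Conclusion.** The rules are incompatible as written, and this is more than missing detail: the stated instructions lead to different reports for the same death. The fatal-AE and Grade 3-5 TEAE endpoints, and the SAE counts, are therefore not determined by the protocol. Removing every death is probably not the intent, but no sentence says so.

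The size cannot be estimated, because the documents give no expected number of on-treatment deaths. The 5-point step is simply one patient in 20 and is no forecast. The conclusion rests on the text alone and on the assumption that sites follow the protocol sentences as written. It should be corrected.

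**What to change.** Put one rule, in the same words, in 2.1, 4.8, 5.2, 5.3, 5.5 and 6.3.5. It should:

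1. say whether progression that is fatal within the safety reporting period is an SAE;
2. treat a death of uncertain cause consistently with the uncertainty sentence in 5.5;
3. settle when worsening tumor signs and symptoms are AEs, so that 5.3 and 5.5 agree;
4. define the fatal-AE endpoint and Grade 5 TEAEs to match.

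Keep the SAE reporting window of 5.2, from consent to at least 28 days after the last dose. Use first dose to 28 days after the last dose only for the TEAE tables.

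Add one table of all deaths from first dose to 28 days after the last dose, by cause: disease, other, uncertain. The result can then be read whichever rule is adopted.

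The cost is protocol wording, one table, a recorded cause for each death in that window, and possibly a few more SAE reports.
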